7.4 Independent Adjudication Committee

An Independent Adjudication Committee will be constituted to provide an independent, external, systematic and unbiased assessment of blinded data to confirm the diagnosis of: 1) investigator reported non-fatal myocardial infarction, non-fatal stroke (hemorrhagic, ischemic, embolic), as well as cardiovascular deaths and 2) investigator reported malignancies during the Phase III trials. The committee will operate in accordance with an Adjudication Committee Charter/Manual of Operations, which will also provide detail on what specific information the committee requires to enable a thorough adjudication.

7.5 Independent Data Monitoring Committee

The Independent Data Monitoring Committee will be responsible for monitoring the safety of the study participants, ensuring that the studies are being conducted with the highest scientific and ethical standards and making appropriate recommendations based on the available data. The IDMC will function independently of all other individuals associated with the conduct of the studies, including the study sponsor AstraZeneca. The committee will operate in accordance with an Independent Data Monitoring Committee Charter (also refer to section

8.5.6). The IDMC will evaluate general safety output including but not limited to wound healing and host defense (infections and infestations). It will also evaluate the output of the independent adjudication committee (major adverse cardiovascular events and malignancies). This will be done in addition to usual pharmacovigilance programs.

8. STATISTICAL ANALYSES BY ASTRAZENECA

8.1 Statistical considerations

- All personnel involved with the analysis of the study will remain blinded until database lock and protocol violators identified
- Analyses will be performed by AstraZeneca or its representatives

Refer to the SAP for additional details.

8.2 Sample size estimate

The study will recruit subjects with blood eosinophil counts $<220/\mu\text{L}$, $220\text{-}299/\mu\text{L}$, and $\geq 300/\mu\text{L}$. The approximately 2:1 ratio between $\geq 220/\mu\text{L}$ and $<220/\mu\text{L}$ allows analysis of the primary population for subjects most likely to respond to benralizumab (i.e. $\geq 220/\mu\text{L}$), while still including subjects below this threshold in order to help understand efficacy and safety in this group. The study is powered for the exacerbation rate comparisons of the subjects with blood eosinophils $\geq 220/\mu\text{L}$ (primary efficacy analysis).

For the primary endpoint annual COPD exacerbation rate, 348 subjects with baseline blood eosinophil counts $\geq 220/\mu\text{L}$ per treatment arm (1392 total) will need to be randomised to achieve 90% power of detecting a 30% reduction in both the 30mg and 100mg benralizumab dose groups versus placebo based on a Hochberg Procedure (Hochberg 1988). This calculation has assumed two-sided 4% alpha level tests, an annual placebo rate of 0.93 events/subject (1.0 events/subject/56 weeks), a negative binomial shape parameter of 0.4, and a dropout rate of 10%. The sample size calculation is based on simulations and has accounted for the power loss from a proposed futility analysis (Section 8.5.6).

As stated previously an approximately 2:1 ratio will be used for subjects with blood eosinophil counts $\geq 220/\mu\text{L}$ and $<220/\mu\text{L}$. Therefore this study will randomise 174 subjects/arm (696 total) with baseline blood eosinophil counts $<220/\mu\text{L}$. An additional 20 subjects/arm will also be recruited to the 220-299/ μL cohort to better characterize patients within this cohort. This addition results in 368 subjects/arm in the $\geq 220/\mu\text{L}$ cohort (1472 total). A total of 2168 subjects are expected to be randomised in this study. Details of the estimated numbers of recruited subjects/arm in each cohort ($<220/\mu\text{L}$, $220\text{-}299/\mu\text{L}$, $\geq 300/\mu\text{L}$) are described in the SAP.

The sample size necessary to achieve a stated power (90% in our case) in this study is calculated based on the estimate of overall exacerbation rate and shape parameter from the negative binomial model (Section 8.5.1). In order to better estimate the overall exacerbation

rate and shape parameter, we plan to conduct a single blinded sample size re-estimation in both studies D3251C0003 and D3251C0004. Blinded estimates of the overall exacerbation rate as well as the shape parameter from data pooled across placebo and all benralizumab doses (for patients with eosinophil counts $\geq 220/\mu\text{L}$) will be used in the sample size re-estimation and strictly no treatment information will be used in the review. The pooled study summaries will not contain any information that would potentially reveal the treatment assignments (e.g., post-randomization eosinophil levels). The review will be conducted before the last patient with eosinophil counts $\geq 220/\mu\text{L}$ is randomized and after the futility analysis (Section 8.5.6). The exacerbation rate and shape parameter will be estimated using the maximum likelihood approach as proposed by [Friede and Schmidli 2010](#). This review may result in an adjustment of sample size. Since this review will be performed in a blinded fashion, no adjustment for the type I error is needed. The blinded data review will be performed by AstraZeneca internal personnel or its designees and the full details of the review will be specified in a blinded data review plan.

8.3 Definitions of analysis sets

8.3.1 All patients analysis set

This analysis set comprises all subjects screened for the study and will be used for reporting of disposition and screening failures.

8.3.2 Full analysis set

All subjects randomized and receiving at least 1 dose of investigational product will be included in the full analysis set, irrespective of their protocol adherence and continued participation in the study. Subjects will be analyzed according to their randomized treatment, irrespective of whether or not they have prematurely discontinued, according to the ITT principle. Subjects who withdraw consent or assent to participate in the study will be included up to the date of their study termination. All efficacy analyses will be analyzed using the full analysis set.

8.3.3 Safety analysis set

All subjects who received at least 1 dose of investigational product will be included in the safety analysis set. Subjects will be classified according to the treatment they actually received. A subject who has on one or several occasions received active treatment will be classified as active. If a subject has received both active doses, then the subject will be classified as the higher active dose. All safety summaries and ADA data will be based on this analysis set.

8.3.4 Pharmacokinetic analysis set

All subjects who received benralizumab and from whom PK blood samples are assumed not to be affected by factors such as protocol violations (e.g., disallowed medication) will be included in the PK analysis set. All PK summaries will be based on this analysis set.

8.4 Variables for analyses

8.4.1 Calculation or derivation of efficacy variables

All efficacy objectives will be evaluated for the 56-week double-blind treatment period, defined as the period after administration of randomised investigational product at Visit 4 and the EOT at Visit 19, inclusive.

8.4.1.1 Exacerbation rate

The annual COPD exacerbation rate will be used as the primary efficacy variable.

A COPD exacerbation is defined in section 5.1.1.

In order to calculate the number of exacerbations experienced by a subject during the 56-week treatment period, the following rule will be applied.

The start of an exacerbation is defined as the start date of systemic corticosteroids or antibiotic treatment or hospital admission, whichever occurs earlier, and the end date is defined as the last day of systemic corticosteroids or antibiotic treatment or hospital discharge, whichever occurs later. In the primary analysis, the number of exacerbations observed for a subject during the 56-week double-blind treatment period will be used as response variable.

Additional systemic corticosteroid treatments, emergency room visits requiring use of systemic corticosteroids, or inpatient hospitalization due to COPD occurring during an exacerbation should not be regarded as a new exacerbation. In order to be counted for as a new exacerbation it must be preceded by at least 7 days in which neither criterion is fulfilled.

Maximum follow-up time for exacerbations for a subject is approximately 56 weeks; defined as the time from randomisation to the date of Visit 19. For a subject lost to follow-up, this will be defined as the time from randomisation to the time point after which an exacerbation could not be assessed.

In the statistical analysis, the number of COPD exacerbations experienced by a subject during the 56-week double-blind treatment period will be used as response variable, and the logarithm of the subject's corresponding follow-up time will be used as an offset in the analysis to adjust for subjects having different exposure times during which the events occur.

For the production of summary statistics, the annual exacerbation rate per subject is calculated, and standardized per 56-week period according to the formula described below.

Annual Exacerbation Rate = Number of Exacerbations*365.25 / (Last follow-up date – Visit 4 date + 1).

For subjects who prematurely discontinue treatment, efforts will be made to continue collecting the exacerbation data until the scheduled Visit 19/ EOT at Week 56 after randomisation (refer to section 3.6.1). In the statistical analysis of exacerbation rate, the data collected up to Visit 19/ EOT at Week 56 will be included for the patients who prematurely

discontinue treatment according to the intent-to-treat principle. For the patients who died during the treatment period the exacerbation data collected up to the date of death will be included in the statistical analysis.

If the cause of death is related to COPD or a COPD exacerbation, the event will also be included in the rate calculation.

8.4.1.2 Proportion of subjects with ≥ 1 COPD exacerbation during 56 weeks of treatment

The proportion of subjects with ≥ 1 COPD exacerbation during the 56 weeks of treatment will be a supportive variable to the primary objective.

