The proposed benralizumab Phase 3 study will evaluate the efficacy and safety of benralizumab in patients who are uncontrolled despite standard of care therapies (double such as ICS/LABA, LABA/LAMA or triple such as ICS/LABA/LAMA) as evidenced by 2 or more moderate exacerbations or 1 or more severe exacerbation(s) in the previous year. Moderate exacerbations are defined as those requiring treatment with systemic steroids and/or antibiotics. Severe exacerbations are defined as those requiring a COPD related hospitalization or result in death. Hospitalization will be further defined as an inpatient admission ≥24 hours in the hospital, in an observation area, the emergency department or other equivalent healthcare facility depending on the country and healthcare system.

Subjects in this Phase 3 study will be stratified by country and blood eosinophil levels (≥300/μL or <300/μL) with a blood eosinophils boundary of ≥220/μL used for the primary and secondary efficacy analyses. Randomization will be capped at the study level for the baseline eosinophil cohorts (<220/μL, 220-299/μL, ≥300/μL) in order to keep predefined cohort sample size and approximately 2:1 ratio of subjects above and below the boundary of 220/μL.

Based on the efficacy observed in CP196 and recent data in the literature (Pascoe S et al 2015), the primary endpoint will be powered and conducted in subjects with blood eosinophil count ≥220/μL. Subjects with lower blood eosinophils levels (<220/μL) will be included to assess the benefit:risk relationship of benralizumab in COPD patients with a broad range of blood eosinophil levels. Descriptive statistics will be used to assess efficacy in COPD subjects across a broad spectrum of eosinophil levels as detailed in the SAP in order to better identify patients who are likely to benefit from benralizumab and also to evaluate inflection points for efficacy and safety to better define which patients need to be treated with this compound.

Three dose levels 10, 30 and 100 mg Q8W benralizumab will be evaluated in this Phase 3 study in COPD subjects, based on PK and eosinophil modelling, observed incidence of ADA, clinical efficacy, and safety.

Since only one dose level was investigated in Study MI-CP196, the dose-efficacy relationship of benralizumab in COPD has not been fully evaluated. Simulations indicate that the Q12W regimen is associated with a broader distribution of peripheral blood eosinophil counts. This

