3.6.1 Procedures for discontinuation of a subject from IP

Subjects who prematurely discontinue treatment should return to the study centre and complete the procedures described for the EOT 12 weeks (± 7 days) after the last dose of IP.

It is highly recommended that all study procedures, including any scheduled visits and ePRO completion, are continued till EOT visit, if possible. The subject will bring the ePRO device to the EOT visit.

At EOT visit the subject will be given two options on how to be followed up:

- The subject should be encouraged to return for all regular clinic and phone call visits until he/she completes a total of 56 weeks in the study. At week 56 all the procedures described for Visit 19 are to be conducted
- If the subject cannot comply or does not wish to comply with the option above, he/she will be offered to be followed up on a monthly basis via phone calls while continuing eDiary completion, until the subject completes 56 weeks in the study. No further procedures will be performed. The subject's decision needs to be documented and the specific section in the ICF addendum needs to be signed.

[figure not shown]
The key elements to be collected are AEs/SAEs, changes in concomitant medications, smoking status and COPD exacerbation information.

The Investigator will be instructed to force data transfer from the ePRO device on the day of EOT visit and then to redispense the device to subject. ePRO alerts will still be in place to notify both the subject and the study center of a potential symptom worsening event (see section 5.1.3.7). The subject will be asked to return the ePRO device to the study centre after the subject completes participation in the study (week 56).

- If the subject refuses the two previous options, he/she will need to sign the specific withdrawal of consent portion of the ICF addendum and return all study materials to the study centre.

AstraZeneca will continue to provide maintenance and rescue medications up to 56 weeks from the time of randomisation (see section 3.5.1) unless the patient withdraws consent. It is the Investigator's responsibility to fully evaluate the patient upon discontinuation or withdrawal to ensure that the patient receives appropriate treatment according to his/her clinical status/ condition.

Figure 2 Premature IP discontinuation

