8.5.1 Primary analysis method(s)

The primary efficacy variable is the annual COPD exacerbation rate and the primary analysis is to compare the annual COPD exacerbation rate of each benralizumab dose group with placebo in subjects with baseline blood eosinophil counts $\geq 220/\mu\text{L}$.

For each of the three benralizumab dose groups, the null hypothesis is that the exacerbation rate on benralizumab is equal to the exacerbation rate on placebo. The alternative hypothesis is that the exacerbation rate on benralizumab is not equal to the exacerbation rate on placebo, i.e.:

H₀: Rate ratio (benralizumab vs. Placebo) = 1

H_a: Rate ratio (benralizumab vs. Placebo) \neq 1

Exacerbation rate in each of the three benralizumab dose groups will be compared to exacerbation rate in the placebo group using a negative binomial model. The response variable in the model will be the number of COPD exacerbations over the 56-week treatment period. The model will include covariates of treatment group, eosinophil cohort (220-299/ μL or $\geq 300/\mu\text{L}$), country, background therapy (ICS/LABA, LABA/LAMA, or ICS/LABA/LAMA), and the number of exacerbations in the year before the study. The logarithm of the follow-up time will be used as an offset variable in the model.

The estimated treatment effect (i.e., the rate ratio of benralizumab versus placebo), corresponding 95% confidence interval (CI), and two-sided p-value for the rate ratio will be presented. In addition, the exacerbation rate and the corresponding 95% CI within each treatment group will be presented.

In addition, the exacerbation rate will also be summarized in subjects with baseline blood eosinophil counts $< 220/\mu\text{L}$, $< 150/\mu\text{L}$, 150-219/ μL , 220-299/ μL , 300-449/ μL , and $\geq 450/\mu\text{L}$ separately for descriptive purpose only.

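### Does the 56-week wording above the annual exacerbation rate formula in section 8.4.1.1 distort the rates that will be reported?

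*Protocol*

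**What the plan says.** Protocol section 8.4.1.1 defines the primary variable in two forms. For inference, the response is the subject's count of exacerbations, with log follow-up time as an offset. For summary tables, "the annual exacerbation rate per subject is calculated, and standardized per 56-week period according to the formula described below". The formula that follows begins "Annual Exacerbation Rate = Number of Exacerbations*365.25" and divides by the days from Visit 4 to last follow-up, plus one.

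Section 8.2 gives the planning assumption on both time scales: "an annual placebo rate of 0.93 events/subject (1.0 events/subject/56 weeks").

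Follow-up ends at Visit 19, at the point where exacerbations can no longer be assessed, or at death. On deaths, section 8.4.1.1 adds: "If the cause of death is related to COPD or a COPD exacerbation, the event will also be included in the rate calculation". No minimum follow-up is set, and section 8.3.2 admits every randomised subject who received one dose to the full analysis set.

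On reporting, section 8.5.1 says that "the exacerbation rate and the corresponding 95% CI within each treatment group will be presented", next to the rate ratio from the negative binomial model. It then turns to the eosinophil ranges: "In addition, the exacerbation rate will also be summarized in subjects with baseline blood eosinophil counts" in six listed ranges, for description only. Section 1.2 says of these: "Descriptive statistics will be used to assess efficacy in COPD subjects across a broad spectrum of eosinophil levels as detailed in the SAP".

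**The concern.** There are two separate worries.

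**Scale.** The sentence names a 56-week unit and the formula computes a one-year unit. Section 8.2 shows that the protocol itself treats these as different numbers for the same rate. A programmer who followed the words would use 392, and one who followed the formula would use 365.25. A table could also print a yearly number under a 56-week label.

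**Stability.** The formula gives each subject a rate over that subject's own follow-up. A subject with one event and very short follow-up gets a very large rate. An early COPD death is the clearest case, because it ends follow-up and also counts as an event. If group summaries were plain means of these rates, one such subject could visibly move a small eosinophil range. Those ranges are meant to help show who is likely to benefit.

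**Working it through.** **Scale.** Inputs: 56 weeks = 392 days (393 with the formula's added day), the multiplier 365.25 (section 8.4.1.1), and 0.93 per year against 1.0 per 56 weeks (section 8.2).

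- The protocol's own conversion is reproduced: 1.0 × 365.25/392 = 0.932, which matches 0.93. The multiplier 365.25 therefore belongs to the yearly scale.
- Ratio of the two scales: 392/365.25 = 1.073.
- A week-56 completer with one exacerbation: 365.25/393 = 0.929 by the formula, and 392/393 = 0.997 per 56 weeks.
- The factor 1.073 is the same constant in every arm, so it would cancel from any ratio of descriptive rates.

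**Where the formula is used.** The primary model (section 8.5.1) takes counts with an offset. The futility rule (section 8.5.6) takes rate reductions from that model. The blinded sample size review (section 8.2) takes maximum likelihood estimates of the overall rate and shape parameter. None of them takes the per-subject rate as input.

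**Stability, assuming the rates are averaged.** One subject with one event in 20 days has a rate of 365.25/20 = 18.26. All others are set at 0.93. Arm sizes of 368 (≥220/µL) and 174 (<220/µL) are from section 8.2; 87 is an assumption, half of the lower cohort.

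| Subjects per arm | Mean of rates | Shift | Shift in total events/total time |
|---|---|---|---|
| 368 | (367 × 0.93 + 18.26)/368 = 0.977 | +5.1% | +0.3% |
| 174 | (173 × 0.93 + 18.26)/174 = 1.030 | +10.7% | +0.5% |
| 87 | (86 × 0.93 + 18.26)/87 = 1.129 | +21.4% | +1.1% |

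The last column takes the other subjects at 393 days each. With 90 days of follow-up instead of 20 (rate 365.25/90 = 4.058), the means are 0.9385, 0.9480 and 0.9660, shifts of +0.9%, +1.9% and +3.9%.

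**Simulated arms of 368.** Rate about 0.93 per year, shape 0.4 read as the dispersion, 10% dropout. The timing of dropout is assumed in each case.

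| Dropout pattern | Mean of rates (SD) | Person-time rate (SD) |
|---|---|---|
| Uniform over 392 days | 0.930 (0.070) | 0.931 (0.059) |
| Same, with at least 28 days for all | 0.930 (0.063) | 0.930 (0.059) |
| Uniform, day 14 to 392 | 0.932 (0.061) | 0.932 (0.058) |
| Hazard proportional to the subject's frailty (true rate 0.932) | 0.931 (0.081) | 0.911 (0.058) |

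In the last row the person-time rate is biased low by 0.932 − 0.911 = 0.021, because frail subjects leave early and contribute less time. Root mean square errors: √(0.001² + 0.081²) = 0.081 for the mean of rates, and √(0.021² + 0.058²) = 0.062 for person-time.

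**The case for a change.** The best argument for a change is that the contradiction stands in the current text, concerns the descriptive form of the primary variable, and would take one phrase to remove. Because it is a stated inconsistency, the SAP cannot simply be presumed to fill it. The per-subject form is also fixed in the same sentence, and person-time or a model-based rate would be steadier in the small eosinophil ranges.

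Part of this stands. The 56-week phrase is wrong, and a plain mean of per-subject rates would be the more variable choice.

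The rest does not carry. The sentence hands the calculation to the formula and itself calls the quantity an annual rate. The formula's label and the endpoint's name agree, so an analyst has no realistic route to 392. The instability argument is aimed at an average that section 8.4.1.1 does not name: mean, median and total are all left open. Excluding short follow-up would conflict with the full analysis set in section 8.3.2. The retention rule in section 3.6.1 also works against short follow-up: "The subject should be encouraged to return for all regular clinic and phone call visits". The preference for person-time is a trade of bias for variance, as the last simulated row shows.

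**Conclusion.** No change to the plan is needed. The scale wording is a clerical slip in a sentence whose formula is right. A sponsor who applies the formula reports a correct yearly rate, and the 7.3% gap would appear only if someone set the formula aside in favour of the phrase.

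The stability point depends on three things the protocol does not state: that per-subject rates are averaged, that a subject with an event has follow-up as short as about 20 days, and that the group is small. Where all three hold, one subject could move a descriptive mean by roughly 5% to 21%; at 90 days of follow-up the range is 0.9% to 3.9%. The SAP, which is not at hand, is the ordinary place to name the summary statistic. For the treatment groups, a rate with a confidence interval is already planned beside the offset-adjusted model.

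No rate ratio, p-value, futility decision or sample size changes under either reading.
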